3. STUDY DESIGN

3.1 STUDY DESIGN OVERVIEW

This is a prospective, international, randomised, double-blind, placebo controlled, and multicentre, parallel group phase II study. Patients with bulbar-onset ALS will be recruited in University hospitals in France and Italy. Patients will be randomised in a 2:1 allocation ratio to receive either IFB-088 50 mg/day + riluzole 100 mg/day or placebo + riluzole 100 mg/day.

Patients will be treated for a period of 6 months (26 weeks). Only patients who have consented and meet the inclusion and exclusion criteria will be eligible for participation in the study.

Patients will undergo 8 visits, as illustrated in [Figure 1](#): screening visit (within 2 weeks before V0), baseline visit (V0), visit 1 (V1, 2 weeks \pm 3 days after V0), visit 2 (V2, 4 weeks \pm 4 days after V0), visit 3 (V3, 9 weeks \pm 4 days after V2), visit 3bis (V3bis, 6.5 weeks \pm 4 days after V3), visit 4 (V4, 13 weeks \pm 4 days after V3), and a follow-up (FU) visit (V-FU, 4 weeks \pm 1 week after V4). In addition to these hospital visits, patients will undergo urine analysis (dipstick) and blood sampling for measurement of creatinine one week after V0, as well as blood sampling for measurement of creatinine and calculation of eGFR at months 2, 4 and 5; these exams can be done in any laboratory, depending on the patient's choice. In case of premature study discontinuation, a final visit (premature discontinuation visit) will take place as soon as possible and no later than 4 weeks after the last investigational medicinal product (IMP) intake. A detailed list of procedures performed at each visit is presented in [Sections 3.7](#) and [4](#).

[figure not shown]
During the screening visit, patient eligibility will be assessed. Patients will be randomised at the baseline (V0) visit after confirmation of eligibility. Safety will be monitored over all the course of the study by a DSMB.

The study will be submitted for approval to the independent ethics committees (IECs) and signed informed consent will be obtained from all patients before any study procedures are conducted.

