5.3 WITHDRAWAL OF THE PATIENT

Patients may withdraw from the study at any time without having to provide justification and without penalty to their continuing medical care.

The investigators may withdraw patients from the study for the following reasons:

- Patient withdrawing the consent,
- If, in the investigator's opinion, continuation in the study would be detrimental to the patient's well-being, in particular in case of an AE,
- If, in the investigator's opinion, the patient is unable to maintain the schedule or is non-compliant,

¹¹ Decline will be calculated as follows: 48 minus ALSFRS-R score at the time of inclusion divided by number of months since occurrence of first symptoms of disease, as reported by the patient.

- If the patient becomes pregnant during the study,
- If the patient meets one of the following criteria for permanent drug discontinuation:
 - Increased ALT or AST levels $\geq 5 \times$ ULN.
 - ALT or AST > 3 ULN and total bilirubin levels > 2 ULN.
 - Neutropenia.
 - Symptoms evocative of interstitial lung disease: dry cough and/or dyspnoea, bilateral diffuse lung opacities.
- Lost to FU. A participant will be considered lost to FU if he/she repeatedly fails to return for scheduled visits and is unable to be contacted by the study site. Site personnel are expected to make diligent attempts to contact participants who fail to return for a scheduled visit or are otherwise unable to be followed up by the site.

The date of withdrawal and the principal reason for withdrawal must be recorded in the eCRF and in the patient's records. No additional data will be collected for withdrawn patients. Every effort must be made to contact patients who did not come back for a planned visit/contact.

Every effort will be made to ensure that patients who do not complete all study visits return to the site for the premature discontinuation visit ([Section 4.1.9](#)), as soon as possible and no later than 4 weeks after the last IMP intake. Patients who withdraw due to an AE or SAE will be given appropriate care under medical supervision until the symptoms resolve or the patient's condition becomes stable.

Patients who prematurely withdrew from the study or are lost to FU will not be replaced by new patients.

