5.12.3.3 Analysis

Clinically significant abnormalities in laboratory values across the whole study will be summarized and listed.

For urinalysis parameters:

Shift tables in relation with normal, abnormal CS and abnormal NCS value from baseline to V3 and V4 will be presented for each parameter.

Urinalysis data will also be listed separately for each parameter.

For 24h protein test parameters:

Shift tables in relation with normal, abnormal CS and abnormal NCS value from baseline to V3 and V4 will be presented for the investigator's overall assessment.

STATISTICAL ANALYSIS PLAN			
InFlectis BioScience	Sponsor:	InFlectis BioScience	
	Protocol Number:	P288ALS	
VERSION 1.0 NOV 12, 2024			

A listing will also be presented for patients with at least one abnormal clinically significant of 24h protein test during the study.

For hematology, biochemistry, renal function, liver function and electrolytes parameters:

Each measurement (continuous data) will be categorized as below, within, or above normal range, based on ranges supplied by the laboratory used. Shift tables in relation to the normal range from Baseline to V3 and V4 will be presented for each parameter.

Laboratory data will also be listed separately for each parameter (indicating abnormal values at each applicable follow-up time point). Quantitative value at each visit with the change from baseline and relative change from baseline will be also presented in the listing.

Table 4: Specific rules for ULN and LLN by parameters

Parameter	Units	Below normal range	In normal range	Above normal range
Glomerular Filtration Rate	ml/min/1,73 m ²	<90	≥90	NA
Basophils	10 ³ /mm ³ ou 10 ³ /uL ou 10 ⁹ /L ou G/L	NA	<0.1	≥0.1
	%	Not analysable (will be converted by data management)		
Eosinophils	10 ³ /mm ³ ou 10 ³ /uL ou 10 ⁹ /L ou G/L	NA	<0.4	≥0.4
	%	Not analysable (will be converted by data management)		
Erythrocytes	10 ¹² /L, 10 ⁶ /mm ³ , 10 ⁶ /uL, T/L	<3.8	[3.8 ;5.5]	>5.5
Hemoglobin	g/dL	<12	[12 ;16]	>16
	g/L	<120	[120 ;160]	>160
Lymphocytes	10 ³ /mm ³ ou 10 ³ /uL ou 10 ⁹ /L ou G/L	<1,5	[1,500 ; 4]	>4
	%	Not analysable (will be converted by data management)		
Monocytes	10 ³ /mm ³ ou 10 ³ /uL ou 10 ⁹ /L ou G/L	<0.5	[0.5 ; 0.8]	>0.8
	%	Not analysable (will be converted by data management)		
Neutrophils	10 ³ /mm ³ ou 10 ³ /uL ou 10 ⁹ /L ou G/L	<1.5	[1.5 ; 7]	>7
	cells/mm ³	<1500	1500 et 7000	>7000

STATISTICAL ANALYSIS PLAN				
InFlectis BioScience	Sponsor:		InFlectis BioScience	
	Protocol Number:		P288ALS	

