VERSION 1.0 NOV 12, 2024				

	%	Not analysable (will be converted by data management)		
White blood cells, total	1000/uL, 10 ³ /mm ³ , 10 ³ /uL, 10 ⁹ /L et G/L	<4.5	[4.5 ; 11]	>11
Glucose	mg/dl	<70	[70 ; 110]	>110
	mmol/L	<4	[4 ; 6.1]	>6.1
	umol/L	<400	[400 ; 610]	>610
HDL cholesterol	g/L	<0.4	≥ 0,4	NA
	mg/dl	<40	≥ 40	NA
	mmol/L	<1.04	≥ 1.04	NA
LDL cholesterol	mg/dL	NA	<160	≥160
	mmol/L	NA	<4.1	≥4.1
Total Cholesterol	mg/dL	NA	<200	≥200
	mmmol/L	NA	<5	≥5
Triglycerides	g/L	NA	≤1.5	>1.5
	mg/dL	NA	≤150	>150
	mmol/L	NA	<1.71	>1.71
	umol/L	NA	<=171	>171
Alanine Aminotransferase	All units	NA	<ULN	>ULN
Aspartate Aminotransferase	All units	NA	≤ULN	>ULN
D-Dimers	All units	NA	≤ULN	>ULN
Direct Bilirubin	All units	NA	≤ULN	>ULN
Gamma Glutamyl Transferase	All units	NA	≤ULN	>ULN
Other parameters	All units	<LLN	[LLN ; ULN]	>ULN

If LLN is missing then all values below the ULN will be considered as in reference range.

If ULN is missing then all values above the LLN will be considered as in reference range.

If a value is <xx then:

- If the LLN = 0 or missing or NA then consider the value as in reference range
- Else consider the value as low reference range

If a value is >xx then:

- If the ULN is missing or NA then consider the value as in reference range
- Else consider the value as upper reference range

For Glomerular Filtration Rate:

If a value is >xx with xx<90 then consider value as below reference range

If a value is >xx with xx≥90 then consider value as in reference range

If a value is <xx then consider value as below reference range

STATISTICAL ANALYSIS PLAN		
InFlectis BioScience	Sponsor:	InFlectis BioScience
	Protocol Number:	P288ALS
VERSION 1.0 NOV 12, 2024		

Note: for all listing value of premature discontinuation and V3bis visit will be also presented when applicable.

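### When a laboratory's upper limit of normal is missing, the SAP codes results that depend on it as in range, so a high value can enter the safety shift tables as normal

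*SAP*

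**What the plan says.** SAP 5.12.3.3 sets out how blood results are classed: "Each measurement (continuous data) will be categorized as below, within, or above normal range, based on ranges supplied by the laboratory used". Table 4 then gives specific rules. Some parameters have fixed cut-offs, some are judged against the ULN alone, and a final row for other parameters uses the laboratory's LLN and ULN.

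Below Table 4 come the rules for missing limits. For a numeric result: "If ULN is missing then all values above the LLN will be considered as in reference range". For a result reported only as greater than a stated figure: "If the ULN is missing or NA then consider the value as in reference range". Mirror-image rules cover a missing LLN. There is no class for a result that cannot be judged.

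The classes feed this output: "Shift tables in relation to the normal range from Baseline to V3 and V4 will be presented for each parameter". The same section also provides other routes to the data: "Quantitative value at each visit with the change from baseline and relative change from baseline will be also presented in the listing", and "Clinically significant abnormalities in laboratory values across the whole study will be summarized and listed".

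**The concern.** A missing ULN means that nobody recorded what counts as high for that result. Coding it as in range assigns an answer the data do not contain. At a post-baseline visit the error runs only one way: it can turn a high value into a normal one, never the reverse.

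The greater-than rule is harder to defend. Such a result is typically at the top of what the laboratory can report, yet it is classed as normal when the limit is missing. The rule names a missing limit and a not-applicable limit separately and then treats them alike. Only the second justifies an in-range class, and Table 4 already marks the parameters concerned (eGFR and HDL cholesterol).

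Safety is the primary objective, and renal toxicity is an adverse event of special interest (Protocol 7.4). Under SAP 5.12.3.2 and 5.12.3.3 the numeric values of these blood parameters go to listings. For most of them the shift table is therefore the planned range-based summary. Only triglycerides and eGFR also get a class table (SAP 5.12.1.2).

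**Working it through.** **The plan's own figure.** The documents give no figure for missing limits. Their only safety-detection figure is in SAP section 3: the chance of at least one SAE among 28 IFB-088 patients is 1 − 0.95^28 = 0.762 at 5% incidence and 1 − 0.90^28 = 0.948 at 10%. Both reproduce. The figure concerns SAEs and is used below only as a yardstick.

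**Step 1. Which parameters depend on a laboratory ULN (Table 4).**

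| Group | Effect of a missing ULN |
|---|---|
| Fixed cut-offs (eGFR, triglycerides, glucose, cholesterols, neutrophils and most other haematology) | None |
| ULN-only rows: ALT, AST, GGT, direct bilirubin | Greater-than results coded in range; plain numbers undefined, because the rule refers to an LLN that Table 4 sets as NA |
| D-dimers (also ULN-only) | None on shift tables: measured only at V3bis (SAP 5.12.3.1.2) |
| Other parameters: creatinine, total bilirubin, ALP, LDH, CK, troponin T and others | Every value above the LLN coded in range |

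**Step 2. The rules applied literally to invented results.**

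| Result | Limits on file | SAP class |
|---|---|---|
| Creatinine 400 | 60 to 110 | High |
| Creatinine 400 | LLN 60, no ULN | In range |
| Creatinine 40 | LLN 60, no ULN | Low |
| CK >20000 | LLN 30, ULN 190 | High |
| CK >20000 | LLN 30, no ULN | In range |
| ALT >1000 | LLN NA, no ULN | In range |
| ALT 400 | LLN NA, no ULN | Rule silent |

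**Step 3. Effect on the shift table.** Let m be the share of results with a missing ULN. The documents do not give it; 2% to 20% is assumed. A patient newly high at V3 or V4 is lost with probability m. For a patient truly high at both visits, with missingness independent between visits:

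| ULN missing at | Tabulated shift | Probability | m = 2%, 5%, 10%, 20% |
|---|---|---|---|
| Baseline only | In range to high (false worsening) | m(1 − m) | 2.0%, 4.8%, 9.0%, 16.0% |
| Later visit only | High to in range (false normalisation) | m(1 − m) | 2.0%, 4.8%, 9.0%, 16.0% |
| Both | In range to in range (hidden twice) | m² | 0.04%, 0.25%, 1.0%, 4.0% |

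Either false shift has probability 2m(1 − m) = 3.9%, 9.5%, 18.0%, 32.0%. If one laboratory's limit is missing at all visits or none, false shifts vanish and the high value is hidden at both visits with probability m.

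**Step 4. Weight of one patient.** Fifty patients randomised 2:1 gives about 33 and 17. One miscoded patient moves a cell by 1/33 = 3.0 points on IFB-088 or 1/17 = 5.9 points on placebo. With the 28 and 14 evaluable patients the steps are 1/28 = 3.6 and 1/14 = 7.1 points.

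**Step 5. The yardstick applied to a high laboratory value.** The chance of tabulating at least one high value among 28 is 1 − (1 − p(1 − m))^28, where p is the true incidence.

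| p | m = 0 | 2% | 5% | 10% | 20% |
|---|---|---|---|---|---|
| 5% | 76.2% | 75.5% | 74.4% | 72.5% | 68.1% |
| 10% | 94.8% | 94.4% | 93.9% | 92.9% | 90.3% |

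**The case against.** The strongest reply is that the rule is a last-resort fallback. Protocol 13.2 already has missing values queried with the site. Protocol 4.2.1.7 requires investigator comment on values beyond normal thresholds, and Protocol 4.2.1.1 makes clinically significant ones adverse events. The SAP lists raw values and changes and summarises clinically significant abnormalities. Nothing in the documents shows that any ULN is in fact missing. All of this stands and limits the harm. It does not correct the shift table, and the abnormal-value flags in the listings may use the same coding.

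Several stronger readings are tempting, and the documents do not support them:

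- **That any laboratory result is affected.** Fixed cut-offs need no laboratory ULN, and results below the LLN stay low.
- **That every ALT, AST, GGT or direct bilirubin result without a ULN is explicitly coded normal.** That is explicit only for greater-than results. For plain numbers it is the likely programming choice, but the text does not settle it.
- **That D-dimers are miscoded in the shift tables.** They have no baseline, V3 or V4 value.
- **That free choice of laboratory feeds the problem.** The sentence in Protocol 3.1, "these exams can be done in any laboratory, depending on the patient's choice", concerns the extra tests one week after V0 and at months 2, 4 and 5, which are not in the V3/V4 tables. The relevant support is Protocol 4.2.1.7 and Table 3, which send safety bloods to local laboratories.
- **That a patient meeting the protocol's discontinuation criteria would commonly be shown as normal.** Criteria such as "ALT or AST > 3 ULN and total bilirubin levels > 2 ULN" are multiples of the ULN, so a site applying them has it. The limit would have to be left out of the eCRF and the query would have to fail. Exclusion criterion 4 likewise requires the ULN for AST, ALT and total bilirubin at screening.

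**Conclusion.** The point holds within its scope. For parameters classed by a laboratory ULN, the stated rule gives a wrong class when that limit is missing and the value is truly high, and the baseline-to-V3/V4 shift tables inherit it. This is an explicit instruction with a wrong result, not just a lack of detail.

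The size cannot be fixed from the documents. One patient is worth 3.0 or 5.9 points in a cell. The probabilities above rest on an assumed m of 2% to 20%, and those for false shifts also on independence between visits. That assumption may well fail where one laboratory serves a site throughout. A reader might infer that toxicity would disappear from the report. It would not, because the listings, the clinically-significant summary and adverse event reporting are separate routes. Severity is minor to moderate.

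**What to change.** Replace the missing-limit rules in SAP 5.12.3.3:

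1. Where the limit needed to class a result is missing, recover it by data query from the same laboratory before database lock. Protocol 13.2 already provides for queries.
2. For a greater-than result, compare the reported figure with the recovered limit.
3. Where no limit can be recovered, class the result as not classifiable, show it in its own row, leave it out of the percentage denominator, and report counts by arm and visit.
4. Keep the in-range class only where Table 4 sets the upper limit as NA (eGFR at or above 90, HDL cholesterol).
5. Treat a missing LLN the same way, and state the rule for plain numeric results in the ULN-only rows.

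Table 4 has a precedent: differential counts in percent are marked as not analysable until data management converts them.

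The cost is SAP wording, some programming and a round of queries, with no protocol amendment or new patient assessments. After lock, the change would go into the addendum described in SAP section 5. The downside is that a few results move to a not-classifiable row.

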4.1.2 Baseline – V0 visit

The baseline visit (V0) will occur 2 days to 2 weeks after the screening visit.

The following assessments will be conducted before the randomisation:

- Confirmation of patient eligibility to the study (as in screening visit, see [Section 4.1.1](#)),
- Delivery of patient card,
- Physical examination and vital signs assessment, according to [Sections 4.2.1.2](#) and [4.2.1.5](#),
- Weight and calculation of BMI,
- Query for changes in concomitant medications,
- Ensure that the patient is still willing to follow the protocol procedures and the visits schedule,
- Urine pregnancy test in females of childbearing potential (WOCBP)⁶. In addition to tests performed at hospital visits, pregnancy tests will be performed at monthly intervals during

⁵ The sniff test is optional. It will be performed only in sites that have the equipment and resources to perform this test.

⁶ High sensitivity urine pregnancy test must be used (sensitivity 25 mIU/ml or more).

treatment and until the end of relevant systemic exposure. If a positive result is detected with urine pregnancy test, a serum pregnancy test will be performed to confirm the results.

- 12-lead ECG ([Section 4.2.1.6](#)), blood and urine samples collection for haematology, blood chemistry, and urinary analysis according to [Section 4.2.1.8](#), will not be repeated unless any intercurrent event might have modified eligibility criteria,

Once patient eligibility is confirmed:

- Recording of AEs (if any),
- Randomisation and treatment allocation,
- Dispensation of study product to the patient,
- Patients will be given a prescription for urine analysis (dipstick for quantification of blood, leukocytes, pH, glucose, and proteinuria) and blood sampling (creatininemia) to be performed at V0 + one week in a local laboratory. Analyses will be performed according to [Section 4.2.1.8](#). Results of these analyses will be sent to the site in real time.
- Instructions to the patient:

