5.2 Derived Data

This section describes the derivations required for statistical analysis. Unless otherwise stated, variables derived in the source data will not be re-calculated.

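### The SAP codes an eGFR printed as '>60' as below normal, although that result says nothing about the limit of 90, so the eGFR shift table can hide real declines or show false ones.

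*SAP*

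**What the plan says.** SAP Table 4 (section 5.12.3.3) gives eGFR two usable categories: under 90 is below range, 90 or more is in range, and the upper category is not applicable. Two GFR-specific rules for right-truncated results follow the table: "If a value is >xx with xx<90 then consider value as below reference range" and "If a value is >xx with xx≥90 then consider value as in reference range". The general rule for other parameters reported as '>xx' points the other way: "If the ULN is missing or NA then consider the value as in reference range".

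Shift tables run from baseline to V3 and V4. Quantitative values, with absolute and relative change from baseline, go into listings. SAP 5.2.22 separately defines six GFR classes, the top two being 59 to under 90 and 90 or more, with no rule for truncated values.

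On the source of the values, SAP 5.2 states: "Unless otherwise stated, variables derived in the source data will not be re-calculated". Nothing is stated for eGFR, and neither document names an eGFR equation. Protocol Table 3 sends the safety serum taken at visits to local laboratories. For the additional tests at week 1 and months 2, 4 and 5, Protocol 3.1 says "these exams can be done in any laboratory, depending on the patient's choice".

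**The concern.** Safety is the primary objective. Crystal nephropathy was the dose-limiting finding in rats (Protocol 1.1.2.1), and renal toxicity is an adverse event of special interest. The eGFR shift table is one of the by-arm laboratory displays a reader would turn to.

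A result of '>60' is a lower bound. It is compatible with 61 and with 110, so it cannot support a statement about 90. Coding it low makes the category depend on how the laboratory prints the number. With only two usable categories, a patient coded low at baseline has no worse category to move to, so the table cannot record deterioration in that patient.

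**Working it through.** The plan gives no figure on this point to reproduce, so the check is mainly one of logic.

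**Step 1. Apply the Table 4 rules to one true value under three print formats.**

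| True eGFR | Printed in full | Laboratory truncates at 90 | Laboratory truncates at 60 |
|---|---|---|---|
| 110 | in range | '>90': in range | '>60': **below** |
| 95 | in range | '>90': in range | '>60': **below** |
| 75 | below | 75: below | '>60': below |
| 45 | below | 45: below | 45: below |

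Only true values of 90 or more are miscoded. A true 60 to 89 printed '>60' reaches the right category by chance.

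**Step 2. Carry this into the shift table.**

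- Stable 95, printed in full at baseline and '>60' at follow-up: in range to below, a false new abnormality.
- Stable 95, '>60' at baseline and printed in full at follow-up: below to in range, a false improvement.
- True fall from 110 to 65, '>60' both times: below to below. The real move through 90 is lost, with no change of laboratory.
- True fall from 110 to 45, '>60' then 45: below to below. The fall is lost in this table, although 45 is visible in the class table and the listing.

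**Step 3. Other eGFR outputs.** '>60' is compatible with both of the top two classes of SAP 5.2.22, so it cannot be assigned. Change and relative change from baseline cannot be computed from it.

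**Step 4. Possible size, by assumption only.** The documents give neither the eGFR distribution nor the share of truncated results. Assume eGFR is normal with mean m (80 to 100) and SD s (12 to 20), restricted to 60 or more in line with the entry criterion. The share of '>60' results that are really 90 or more is

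P = [1 − Φ((90 − m)/s)] / [1 − Φ((60 − m)/s)].

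- Lowest, m = 80, s = 12: P = 0.212.
- Highest, m = 100, s = 12: P = 0.798.

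If a share q of results comes from laboratories that truncate at 60, then q × P of all results are falsely low. For the 28 evaluable active patients planned, that is 28 × q × P per visit:

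| q | Falsely low, all results | Of 28 active patients |
|---|---|---|
| 10% | 2% to 8% | 0.6 to 2.2 |
| 25% | 5% to 20% | 1.5 to 5.6 |
| 50% | 11% to 40% | 3.0 to 11.2 |

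If no laboratory truncates (q = 0), the effect is nil.

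**The case against.** The case for leaving the rule alone is that it errs towards flagging, affects one descriptive display, and may never be triggered. Much of this limits the point, and three stronger readings should be set aside.

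- **That the patient's free choice of laboratory drives the shift-table error.** That choice covers only week 1 and months 2, 4 and 5. The shift tables use baseline, V3 and V4, whose samples go to the local laboratories of Protocol Table 3. A false new shift needs the print format to change between those visits, which the documents neither show nor exclude. A hidden shift needs no such change.
- **That a real decline cannot be seen at all.** Creatinine is a separate renal parameter with its own categories, shift table and listing of change from baseline. Blood urea nitrogen and the urinary measures are also reported.
- **That the renal safety assessment as a whole depends on the rule.** Renal events of special interest and clinically significant abnormalities rest on investigator reporting and judgement. Eligibility is not affected by a '>60' print either.

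It is also fair that randomisation and blinding give no reason to expect truncation to differ systematically by arm. The existence of the rule shows that the case was provided for, not how often it occurs.

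The claim that the rule is cautious does not stand. It flags at follow-up after a numeric baseline, but at baseline it does the opposite and removes the patient from the count of possible deteriorations.

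**Conclusion.** The rule is logically wrong and should be replaced. Followed as written, it assigns 'below range' to every eGFR printed '>xx' with xx under 90. Those truly at 90 or more are misclassified, so the baseline-to-V3/V4 shift table can err in both directions.

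The reach is limited to the descriptive eGFR shift table, class table and listings. The size is unknown: the range of 21% to 80% of '>60' results rests on assumed distributions, and the share of truncated results is not documented. A reader might infer that almost every eligible patient at a truncating laboratory is wrongly coded. That does not follow, because under the same assumptions about 20% to 79% of such results are truly below 90 and are coded correctly.

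**What to change.** In SAP 5.2.22 and 5.12.3, derive eGFR from creatinine (units harmonised), age and sex, using one named equation for all visits including months 2, 4 and 5. Use the derived value for the classes, the shift tables and change from baseline, and list the laboratory-reported value beside it. The protocol already collects all the inputs, and the SAP already takes this approach for SVC percent predicted.

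Replace the rule for '>xx' with xx below 90 by 'not classifiable' for any value that cannot be recalculated. Deleting it is not enough: the general rule would then apply ("If the ULN is missing or NA then consider the value as in reference range"), and '>60' would be called normal with no better support.

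Separately, add creatinine at V0 + 1 week to the visit note in SAP 5.12.3.2, which lists only the urine dipstick there. Protocol 4.1.2 prescribes "blood sampling (creatininemia) to be performed at V0 + one week in a local laboratory".

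The cost is SAP wording, unit harmonisation and one derived variable, with no new data. Some derived values will differ from the printout the site saw, which is why both should be listed. Recalculation removes differences in equation and print format, but not differences in how laboratories measure creatinine.
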